[figure not shown]

Amendment 1 (v2.0)	28SEP2022	
Updates to be consistent with protocol superseded amendment 2:
 

Renamed mucosal healing secondary and exploratory endpoints to combined endoscopic and histologic remission

Added Change from baseline in partial Mayo score at each assessment through week 12 for the phase 2 Induction period exploratory endpoint.

Updated Corticosteroid-free clinical remission at week 52 endpoint to be for subjects receiving corticosteroids at randomization, original endpoint was for subjects receiving corticosteroid at week 12

Replaced rectosigmoidoscopy with endoscopy throughout

Updated study design language in regards to ending IP, early termination visit, safety follow up visit, and entry into the long term extension study.

Updated DMC meeting frequency

Updated language for disease worsening criteria during long term treatment period

 
● Updated Full Analysis Set to include all randomized subjects
 
Other updates:
 

Updated the definition for actual treatment group in the overall study period to be a combination of the actual treatment group in the induction period and actual treatment group in the long term treatment period

Added 'study day 90' in definition of Induction Adverse event exposure period and end of induction date.

Updated definition for exposure adjusted adverse event analysis to include all events up to EOS

Updated baseline definition for fecal calprotectin

		

• Updated the method of analysis for subject accountability to summarize the induction period and overall study period separately

• Added medical history and procedures to the imputation rules in Appendix C

• Added Overall summary of subject incidence of treatment-emergent adverse events and by preferred term and worst severity grade will be provided by anti-AMG592 and Anti-IL-2 antibody status.

Amendment 2 (v3.0)	19FEB2025	
Updates to be consistent with protocol amendment 3, 4 and decision of IA3 to terminate the study:
 

• Sample size reduced to 240 from 320

• Clarified definition of intercurrent events

• Added definitions for Endoscopic Remission, Clinical Remission and Clinical Response based on local endoscopy score

• Added Appendix D: Mayo Score Categories

• Select exploratory endpoints removed

• Covariate and subgroup analyses removed

• Other administrative updates

## List of Abbreviations

Abbreviation	Explanation
ANCOVA	Analysis of Covariance
ASA	Aminosalicylates
COVID-19	Coronavirus disease 2019
CTCAE	Common Terminology Criteria for Adverse Events
DAP	Data Access Plan
DMC	Data Monitoring Committee
ECG	Electrocardiogram
eCRF	Electronic Case Report Form
FAS	Full Analysis Set
FDA	Food and Drug Administration
GSO-DM	Global Study Operations-Data Management
hsCRP	High Sensitivity C-reactive Protein
IBG	Independent Biostatistics Group
IL-2	Interleukin-2
IRT	Interactive Response Technology
IV	Intraveneous(ly)
JAK	Janus kinase
NCT	National Clinical Trials
PGA	Physician's Global Assessment
PRO	Patient Reported Outcome
QTc interval	QT interval corrected for heart rate using accepted methodology
SAP	Statistical Analysis Plan
TEAE	Treatment Emergent Adverse Event
TNF	Tumor Necrosis Factor
UC	Ulcerative Colitis

## 1. Introduction

The purpose of this Statistical Analysis Plan (SAP) is to provide details of the statistical analyses that have been outlined within the protocol **superseded** amendments **3 and 4** for study 20170104, Efavaleukin Alfa dated **21 August 2024**. The scope of this plan includes the primary analysis and the final analysis that are planned and will be executed by the Amgen Global Biostatistical Science department unless otherwise specified.

## 2. Objectives, Endpoints and Hypotheses

### 2.1 Objectives and Endpoints/Estimands

Objectives	Endpoints
Primary	

To evaluate the effect of efavaleukin alfa on induction of clinical remission

	

Clinical remission at week 12

Primary Estimand	
Variable: Clinical remission at week 12	
Estimator: Difference in clinical remission rates	
Population: All subjects with moderately to severely active UC with inadequate response, loss of response, or intolerance to at least 1 of the following: conventional therapy, biologics, or targeted small molecules, who are randomized and received at least 1 dose of investigational product.	
Treatments: Each efavaleukin alfa dose group and placebo.	
Intercurrent event – composite variable strategy: Subjects will be considered as not meeting the endpoint if:	

They initiate or increase the dose of UC related protocol-prohibited medication or concomitant UC medication between the date of the screening endoscopy and the week 12 endoscopy.

Discontinuation of investigational product on or prior to the end of induction period.

A colectomy (partial or total) or an ostomy.

	
Secondary	

To evaluate the effect of efavaleukin alfa on induction of clinical response

	

Clinical response at week 12

To evaluate the effect of efavaleukin alfa on induction of endoscopic remission

	

Endoscopic remission at week 12

• To evaluate the effect of efavaleukin alfa on induction of symptomatic remission

	

• Symptomatic remission at week 12

• To evaluate the effect of efavaleukin alfa as induction therapy on combined endoscopic and histologic remission

	

• Combined endoscopic remission and histologic remission of the colon tissue at week 12



• To evaluate the effect of efavaleukin alfa as induction therapy on change in histological score

	

• Change from baseline in histological score at week 12 as measured by Geboes score

• To evaluate the safety and tolerability of efavaleukin alfa

	

• Treatment-emergent adverse events

UC = ulcerative colitis

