
Intercurrent event – composite variable strategy: Subjects will be considered as not meeting the endpoint if they meet any of the following criteria prior to the week 12 visit:
 
• Initiation of or change in protocol-prohibited medication or concomitant UC medication• A colectomy (partial or total) or an ostomy• Discontinuation of investigational product	
Secondary	

• To evaluate the effect of efavaleukin alfa on induction of clinical response	
• Clinical response at week 12

• To evaluate the effect of efavaleukin alfa on induction of endoscopic remission	
• Endoscopic remission at week 12

• To evaluate the effect of efavaleukin alfa on induction of symptomatic remission	
• Symptomatic remission at week 12

• To evaluate the effect of efavaleukin alfa as induction therapy on combined endoscopic and histologic remission	
• Combined endoscopic remission and histologic remission of the colon tissue at week 12

• To evaluate the effect of efavaleukin alfa as induction therapy on change in histological score	
• Change from baseline in histological score at week 12 as measured by Geboes score

• To evaluate the safety and tolerability of efavaleukin alfa	
• Treatment-emergent adverse events

UC = ulcerative colitis

Overall Design

This phase 2 dose-finding study is a multicenter, randomized, double-blind, placebo-controlled, parallel-group, 12-week induction study of efavaleukin alfa in subjects with moderately to severely active UC who have failed at least 1 of the following: conventional therapy (eg, immunomodulators, corticosteroids), biologic therapy, or targeted small molecule. This study will be used to establish the efavaleukin alfa induction dose and maintenance dose/dosing regimens for continued development.

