6.2.2 Dosage Adjustments, Delays, Rules for Withholding or Restarting, Permanent Discontinuation

6.2.2.1 Amgen Investigational Product: Efavaleukin Alfa

No dosage adjustments will be allowed during the study. Subjects will be permanently discontinued from investigational product if they initiate excluded treatments as described in Section 6.1.6 at any time during the study.

Refer to Section 7 for handling permanent discontinuation of investigational product.

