8.1 General Study Periods

8.1.1 Screening, Enrollment and/or Randomization

Visit assessments for screening, enrollment, randomization, and day 1 dose administration will occur per the Schedule of Activities ([Table 1-1](#)).

Informed consent must be obtained before completing any screening procedure or discontinuation of standard therapy for any disallowed therapy. After the subject has signed the ICF, the site will register the subject in the IRT and screen the subject in order to assess eligibility for participation. The screening window is up to 35 days prior to first dose of investigational product.

All screening evaluations must be completed and reviewed to confirm that potential subjects meet all eligibility criteria. The investigator will maintain a screening log to record details of all subjects screened and to confirm eligibility or record reasons for screening failure, (see Section [5.4](#)) as applicable.

A subject must be in screening for at least 14 days prior to day 1 to enable a minimum of 7 days of Mayo daily symptom diary collection prior to the screening endoscopy and to

enable results from the central reader assessment of the endoscopy to be received prior to the day 1 visit. Stool frequency and rectal bleeding Mayo subscore calculation, laboratory results from blood collection, stool collection, and urinalysis results must have been received and confirmed eligible prior to subject proceeding to screening endoscopy.

Mayo daily symptom diaries will be provided to each subject to record stool frequency and episodes of rectal bleeding. The daily diaries will be completed from screening and will be used to calculate the stool frequency and rectal bleeding Mayo subscores (Section 8.3.1) to assess the subject's eligibility for further screening and to train the subject on the use of the daily diary (Section 8.3.1.1). Subjects with a combined stool frequency and rectal bleeding subscore ≥ 2 (using the average of the 3 most recent days in the 7 days prior to initiation of bowel preparation for the screening endoscopy) can proceed with **endoscopy** (Section 8.3.1.2). Subjects who do not have an up-to-date colorectal cancer surveillance colonoscopy in source document will have a colonoscopy instead of a rectosigmoidoscopy at screening as per inclusion criteria 105.

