#### **9.5.2 Analyses of Primary Efficacy Endpoint(s)/Estimand(s)**

The primary analysis of the primary efficacy estimand will use the logistic regression model described in [Section 9.5.1.1](#) based on the Full Analysis Set (FAS) described in [Section 6.1](#) and the subjects with missing data will be imputed using nonresponder imputation.

A composite variable strategy will be used to handle intercurrent events for the primary estimand. Subjects will be considered as not meeting the endpoint if they meet any of the following criteria:

- Initiation of or **increase the dose of UC related** protocol-prohibited medication or concomitant UC medication **between the date of the screening endoscopy and the week 12 endoscopy**
- **UC related protocol-prohibited medications include:**
  - **Any investigational therapy for Ulcerative Colitis**

- **Biologic agents (eg, Vedolizumab, Ustekinumab, Infliximab, Adalimumab, Golimumab)**
- **T cell depleting agents (eg, Antithymocyte immunoglobulin, Campath [Alemtuzumab])**
- **Recombinant IL-2 (eg, Proleukin [aldesleukin])**
- **Jak Inhibitors (eg, Baricitinib, Tofacitinib, Upadacitinib)**
- **Other immunomodulatory agents (eg, S1P modulators [Fingolimod and siponimod], cyclosporine, Mycophenolic acid, tacrolimus, sirolimus)**
- **Corticosteroids via IV, intramuscular, or rectal route**
- **5-ASAs via rectal route**
- **Concomitant UC medication includes:**
  - **Oral 5-ASA**
  - **Immunomodulators (azathioprine, 6-mercaptopurine, methotrexate)**
  - **Oral corticosteroids**
- Discontinuation of investigational product on or prior to the **end of the induction period**

To assess the impact of the composite variable strategy for the intercurrent events, an additional analysis will be performed using the treatment policy strategy. In this analysis the actual remission status at week 12 will be used, regardless of each intercurrent event. Subjects with missing week 12 remission status will be imputed using nonresponder imputation.

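### The failure rule tests only starting or increasing a prohibited UC drug, so a subject enrolled in breach of eligibility who continues one unchanged, with investigational product not stopped, can count as a remission

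*SAP*

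**What the plan says.** The primary estimand uses a composite strategy. The medication criterion in SAP 2.1 is that subjects fail if "They initiate or increase the dose of UC related protocol-prohibited medication or concomitant UC medication between the date of the screening endoscopy"; the window closes at the week 12 endoscopy. SAP 9.5.2 repeats the criterion and lists the drugs. The protocol (Synopsis and Section 3) words it as "Initiation of or change in protocol-prohibited medication or concomitant UC medication" before the week 12 visit. In both documents one test applies to two kinds of drug: background UC therapy that must stay stable (Protocol 6.7.2.1), and therapy that may not be used alongside IP or at any time in the study (Protocol 6.1.6 and Appendix 8).

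The other failure criteria are colectomy or ostomy and "Discontinuation of investigational product on or prior to the end of induction period". On excluded treatments, Protocol 6.2.2.1 says: "Subjects will be permanently discontinued from investigational product if they initiate excluded treatments as described in Section 6.1.6".

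**The concern.** For a permitted background drug, starting or increasing it is the event that matters, because stable use is expected. For a prohibited drug, any use during induction is what the protocol disallows. A continuous record that begins before the screening endoscopy and runs unchanged to week 12 contains no start and no increase in the window, so the rule does not see it. If that subject reaches week 12 remission, the remission is credited to the assigned arm even though the protocol does not allow that drug with IP.

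SAP 9.5.3 uses the same intercurrent events for the four binary secondary endpoints and for the Geboes score analysis, so the gap carries over to those. Remission counts are likely to be low, so a single misclassified subject is visible in an arm's rate.

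**Working it through.** **1. Does any other rule fail this subject?** Take a prohibited UC drug with a complete start date before the screening endoscopy, continued unchanged to week 12, in a subject with observed remission.

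| Rule | Source | Fails the subject? |
|---|---|---|
| Initiation or dose increase in the window | SAP 2.1, 9.5.2 | No |
| Initiation or change | Protocol Synopsis, 3 | No, use is unchanged |
| Eligibility criteria 220–223, 225 | Protocol 5.2 | Should prevent randomization; does not set endpoint status |
| Mandatory IP stop | Protocol 6.2.2.1 | No, tied to initiating |
| IP discontinued for any reason | SAP 2.1, 9.5.2; Protocol 7.1 | Yes, if IP is in fact stopped |
| Ineligibility found after enrolment | Protocol 8 | Not automatically; the sponsor is consulted on whether treatment continues |
| Full analysis set | SAP 6.1 | No, all randomized except one closed site |
| Important protocol deviations | SAP 9.3 | No, tabulated and listed only |
| Clinical remission definition | SAP 5.5 | No, Mayo scores only |
| Treatment policy analysis | SAP 9.5.2 | No, uses observed status |

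Only an actual IP stop catches the subject.

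**2. Same exposure, different dates.** Under SAP Appendix C, an ongoing drug with a wholly missing start date is assigned the first-dose date. That lies inside the window, so it would read as an initiation. With a complete earlier start date, the same exposure is not flagged. The result then turns on date completeness, not on use.

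**3. How could it arise?** Protocol 8.1.1 requires consent before "discontinuation of standard therapy for any disallowed therapy", so a washout may begin after consent. The screening endoscopy falls about 14 days, and at least 5 days, before day 1 (Protocol 8.3.1.2), within a 35-day screening window.
- Rectal 5-ASA or rectal steroid (2 weeks): 14 + 5 = 19 to 14 + 14 = 28 days, which fits in 35.
- Anti-TNF, anti-integrin or IL-12/23 antibody (8 weeks): at least 56 + 5 = 61 days, which does not fit in 35.

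A washout begun during screening and left incomplete is therefore plausible for the rectal products, not for those biologics.

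**4. Size.** Power and assumed rates are blacked out in both documents, so there is no plan figure to reproduce. Arm size: 240/4 = 60, which agrees with the text.
- One remitter: 1/60 = 1.67 percentage points.
- Assumed placebo rates, from two week 8 trials of another drug cited in Protocol 2.2.1.1: 0.036 × 60 = 2.2 and 0.082 × 60 = 4.9 remitters. Active rates in the same trials: 0.166 × 60 = 10.0 and 0.185 × 60 = 11.1.

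Illustration with assumed counts, unadjusted: d = p1 − p0, SE = √[p1(1 − p1)/60 + p0(1 − p0)/60], interval d ± 1.96 SE. For 11 against 4: d = 0.1833 − 0.0667 = 0.1167, SE = 0.0594.

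| Active / placebo remitters | Difference (points) | 95% interval | p |
|---|---|---|---|
| 11 / 4 | 11.67 | 0.02 to 23.32 | 0.0497 |
| 10 / 4 (one active reclassified) | 10.00 | −1.35 to 21.35 | 0.0841 |
| 9 / 4 (two active reclassified) | 8.33 | −2.69 to 19.35 | 0.1384 |
| 11 / 3 (one placebo reclassified) | 13.33 | 2.10 to 24.57 | 0.0200 |

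The starting counts were chosen close to 0.05 to show sensitivity. They are not a forecast, and the planned model also adjusts for the stratification factors.

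**The case against.** The strongest reply is that this subject should not be in the trial. Criteria 220–223 and 225 exclude recent or current use of these drugs, eligibility is checked at screening and again on day 1, waivers are not given, and concomitant therapy is reviewed throughout induction. This stands, and it limits how often the gap can open. It does not close it, because a failure rule for prohibited medication exists to deal with departures from the protocol.

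Second, a reader might infer from Protocol 6.2.2.1 that IP discontinuation leads to failure only after an excluded drug is initiated. The documents do not support that. The SAP criterion is IP discontinuation for any reason, and Protocol 7.1 lists ineligibility, protocol deviation and non-compliance among possible reasons. A continuing user whose IP is stopped is already a failure. The gap needs use that is missed, or a decision to continue IP.

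Third, such a subject had active disease at screening while on the drug, and the use predates randomization, so it should balance across arms in expectation. This weakens any claim of systematic bias. It does not rule out chance imbalance with a few cases in arms of 60, nor a drug begun shortly before the endoscopy that is still taking effect.

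Fourth, *initiate* is undefined. Separately recorded repeat infusions, or records with imputed start dates, might be flagged already. That stands, and it is itself a reason to define the rule by use.

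Finally, p-values are nominal and the study met futility at the third interim analysis, so the practical stakes are modest.

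**Conclusion.** The point holds in a limited form. As written, the SAP and protocol estimand let a week 12 remission stand for a subject who entered in breach of criteria 220–223 or 225, continued a prohibited UC drug unchanged from a known date before the screening endoscopy, and did not have IP stopped. Each such remitter is worth 1.7 points in an arm of 60. The scale of 2 to 5 placebo remitters rests on rates from another drug's trials, since this trial's assumptions are blacked out. The number affected is not in the documents and is probably small.

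Three stronger readings should not be drawn. The documents do not show that any such subject was enrolled. They do not show that the gap favours efavaleukin alfa; reclassification can move the difference either way. And the SAP did not create the gap by replacing change with increase, because the protocol wording also misses unchanged use.

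**What to change.** Split the medication criterion in SAP 2.1 and 9.5.2:

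- **UC-related prohibited medication, as listed in 9.5.2:** any confirmed use between the screening endoscopy and the week 12 endoscopy is failure, whatever the start date. Keep the current opening of the window. Starting it at day 1 would release a prohibited course begun after the screening endoscopy and ended before day 1, which fails now. Name the list explicitly, because the SAP 5.1 table under the same label is wider and includes live vaccines.
- **Permitted concomitant UC medication:** keep the initiation or dose-increase rule.

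Query records with a missing stop date before counting them as use, since Appendix C otherwise treats them as ongoing. Align the protocol estimand wording. SAP v3.0 (19 February 2025) postdates the August 2024 futility result, so record the change as a clarification or report it as a sensitivity analysis beside the existing rule.

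This concerns endpoint classification only. Protocol 6.1.6 bars certain drugs unless IP has stopped, while 6.2.2.1 ties the mandatory stop to initiation; the sponsor should reconcile those passages.

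Cost: one derivation change and a few data queries. A subject whose late washout ended between the screening endoscopy and day 1 would also become a failure, which is consistent with how a start in that interval is treated now.

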6.7.2.1 Induction Period

The following treatments for UC may not be initiated or have dose increased through end of the induction period (Section 5.1):

- Oral 5-ASA compounds (eg, sulfasalazine, mesalamine)
- Immunomodulators (azathioprine, 6-mercaptopurine, methotrexate)
- Oral corticosteroids including budesonide MMX or beclomethasone dipropionate (gastro-resistant prolonged-release tablet)

Subjects who are receiving any of these treatments for UC at day 1 must keep their prescribed dosage stable throughout the induction period and the therapy can only be discontinued or reduced in dose if in the investigator's clinical judgment it is required because of toxicity or other medical necessity; even if the toxicity resolves, the therapy must not be restarted.

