### 3.3 Adaptive Design

Interim analyses will be conducted to assess for futility. [REDACTED]

[REDACTED]. Futility will be assessed at each interim.  
[\(Section 7.1\).](#)

The interim analyses will be conducted by an external Independent Biostatistics Group (IBG) and results evaluated by an independent DMC. In the case where pre specified decision rules are met at a planned interim analysis, a Data Access Plan (DAP) Team will be invoked. The DAP Team is comprised of a small team of senior members internal to Amgen but external to the study team. To facilitate final decision making, the DAP Team may evaluate unblinded results. Further details will be described in a Data Access Plan.

The study team, investigators and subjects will remain blinded to the results of the IAs unless the DAP team have made the decision to terminate the trial.

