### **11.        Changes From Protocol-specified Analyses**

- The third interim analysis conducted for the study in August 2024 revealed that the study met futility criteria, leading to its termination. As a result of this decision, select exploratory endpoints originally included in the Statistical Analysis Plan (SAP) are being removed. These endpoints will not be discarded entirely; instead, they will be documented in a Supplemental Statistical Analysis Plan (SSAP) and will not be documented in CSR.
- Subject data from site 66164 are not included in the analysis set because the site closed due to noncompliance with the protocol and FDA regulations. The following listings for the affected subjects will be generated separately:
  - Adverse Events
  - Concomitant Medications
  - Laboratory Data

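### SAP v3.0, dated after the futility result, narrows the primary failure rule from any change in UC medication to initiation or dose increase, and SAP Section 11 does not list this

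*SAP*

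**What the plan says.** **Protocol.** The Synopsis and Section 3 give the same composite rule. Among the events that make a subject a non-remitter before the week 12 visit is "Initiation of or change in protocol-prohibited medication or concomitant UC medication". The estimand population is all randomized subjects who meet the disease definition. Section 6.7.2.1 forbids starting or increasing background 5-ASA, immunomodulators or oral corticosteroids during induction. For subjects already on them it adds that "the therapy can only be discontinued or reduced in dose if in the investigator's clinical judgment it is required because of toxicity" or another medical need.

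**SAP v3.0.** Section 2.1 counts failure if "They initiate or increase the dose of UC related protocol-prohibited medication or concomitant UC medication". The window for such events runs from the screening endoscopy to the one at week 12. Section 9.5.2 repeats the rule for the primary analysis ("increase the dose of UC related protocol-prohibited medication or concomitant UC medication"). Section 9.5.3 carries it to the four binary secondary endpoints and to the imputation of the Geboes score. The population in Section 2.1 is subjects "who are randomized and received at least 1 dose of investigational product", whereas Section 6.1 defines the full analysis set (FAS) as all randomized, less one closed site.

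**Timing and record.** Section 11 reports that "The third interim analysis conducted for the study in August 2024 revealed that the study met futility criteria, leading to its termination". The v3.0 entry in the revision history, dated 19FEB2025, describes the edit as a clarification of the intercurrent events. Section 11 lists the removed exploratory endpoints and the excluded site, and nothing on the failure rule.

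**The concern.** The primary endpoint has two failure rules, and the one to be programmed was fixed after the interim outcome was known. The two rules classify the same subject differently: someone who stops azathioprine for toxicity, stays on investigational product and meets the remission criteria at week 12 is a failure under the protocol and a remitter under the SAP. No other failure criterion clearly catches that subject. A reader who looks in the SAP section meant for departures from the protocol would not learn that the rule had moved, and could not tell how far the reported remission rates depend on it.

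**Working it through.** **1. The two rules side by side.**

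| Element | Protocol Synopsis and Section 3 | SAP 2.1 and 9.5.2 |
|---|---|---|
| Trigger | Initiation or any change | Initiation or dose increase |
| Prohibited drugs | All protocol-prohibited | UC-related |
| Window | Before the week 12 visit, no start stated | Screening endoscopy to week 12 endoscopy |
| Population | Randomized | Randomized and dosed (2.1); FAS, all randomized less one site (6.1) |

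**2. Which differences matter.**
- *Trigger.* This is the substantive change. Reductions and stops drop out of the failure rule.
- *UC-related.* This matters little. The table that defines the term in SAP 5.1 largely repeats protocol Appendix 8. The list in SAP 9.5.2 is shorter, but protocol 6.2.2.1 permanently stops investigational product in anyone who starts a treatment excluded under 6.1.6, and stopping product during induction is itself a failure.
- *Window.* The stated start at the screening endoscopy may widen the rule. No net direction can be shown.
- *Population.* SAP 9.5.2 uses the FAS with nonresponder imputation, so an undosed subject with no week 12 data counts as a failure. The wording in 2.1 does not alter the analysis.

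**3. When the edits were made.** The increase, UC-related and window wording is in bold, as are other v3.0 edits such as the sample size of 240. The dosed-only phrase is not bold. The v2.0 history (28SEP2022) records that the FAS was changed to all randomized, so the phrase is probably left over from before then. That is an inference, because the earlier SAP versions are not available.

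**4. Size.** The documents give no count of reductions or stops, and the power statement is not visible. The only plan figure that can be checked is 4 × 60 = 240, which agrees.
- One subject: 1/60 = 1.67 percentage points in that arm.
- Assume that 5–10% of an arm reduce or stop a UC drug and that 10–30% of those are in remission. The arm's rate then shifts by 0.05 × 0.10 = 0.5 points to 0.10 × 0.30 = 3.0 points, or 0.3 to 1.8 subjects of 60.
- If the upper remission rate is instead 18.5%, the higher of the two tofacitinib induction results in protocol 2.2.1.1, the top of the range is 0.10 × 0.185 = 1.9 points, or about 1.1 subjects.

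**5. Effect on the difference between arms (assumed counts, not trial data).** Start from 5/60 on placebo and 11/60 on active, and use the pooled test z = (p_A − p_P) / √[p̄(1 − p̄)(2/60)]. Here p̄ = 16/120 = 0.133 and z = 0.100/0.062 = 1.61, so p = 0.107. The planned analysis is a stratified logistic model, so these values only illustrate sensitivity.

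| Reclassified per affected arm | Active only | Placebo only | Both arms equally |
|---|---|---|---|
| 1 | 11.7 points, p = 0.067 | 8.3 points, p = 0.191 | 10.0 points, p = 0.125 |
| 2 | 13.3 points, p = 0.041 | 6.7 points, p = 0.306 | 10.0 points, p = 0.142 |
| 3 | 15.0 points, p = 0.024 | 5.0 points, p = 0.453 | 10.0 points, p = 0.157 |
| 4 | 16.7 points, p = 0.014 | 3.3 points, p = 0.624 | 10.0 points, p = 0.171 |

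**6. Does the planned additional analysis cover this?** The treatment-policy analysis in SAP 9.5.2 ignores every intercurrent event. Leaving the window aside, the remitter count in each arm is lowest under the protocol rule, higher or equal under the SAP rule, and highest or equal under treatment policy. The additional analysis therefore lies on the far side of the SAP rule from the protocol rule and cannot isolate the change.

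**The case against.** The best defence is that the SAP rule follows the protocol's own conduct rule. Section 6.7.2.1 prohibits starting or increasing UC therapy and tolerates reductions for toxicity or medical need, so counting only starts and increases still captures rescue. That is a plausible reason and the resulting rule is defensible, but neither document states the reason, and the current protocol still says change.

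The edit is also not hidden: it appears in a dated revision history next to the termination decision, and the protocol requires only that the SAP be final before database lock. This stands, and the accurate criticism is narrower. Calling it a clarification understates it, and Section 11 is where it belongs. The history's heading ties the updates to protocol amendments 3 and 4 and the interim decision, yet the rationales for those amendments mention no change to the intercurrent events.

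Two stronger readings are tempting. One is that v3.0 also rewrote the population after futility. The documents do not show this: the phrase is unmarked, the analysis uses the FAS, and the population change that v3.0 does mark, the site exclusion, is listed in Section 11. The other is that the rule was chosen with sight of unblinded results. SAP 3.3 keeps the study team blinded "unless the DAP team have made the decision to terminate the trial", while SAP 7.1 says that they remain blinded and gives no exception. Whether the authors of v3.0 were unblinded is not stated.

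Finally, the p-values are nominal and the trial has already stopped for futility, so no confirmatory claim depends on the rule. This lowers the severity.

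**Conclusion.** The protocol and the SAP conflict on the primary estimand's failure rule. The SAP version post-dates the futility result, carries through to the secondary endpoints, and is missing from Section 11. On the trigger alone, the SAP rule can only leave unchanged or raise each arm's remission rate, by 1.7 points per reclassified subject. The range of 0.5 to 3.0 points per arm rests on assumed rates of dose reduction and remission, and its upper end is generous against the remission rates the protocol cites. Neither the size nor the direction of the effect on the treatment difference can be determined from the documents, so nothing here shows that the edit favours efavaleukin alfa. The dosed-only population in SAP 2.1 is a separate wording conflict with no effect on the analysis as specified. Overall severity is moderate.

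**What to change.** 1. Run the primary analysis under the protocol's rule (initiation or any change before the week 12 visit) and report it beside the SAP version, with the number of subjects per arm whose remission status differs between the two.
2. List the change in SAP Section 11, with its reason and its date relative to the third interim analysis.
3. Delete the condition of at least one dose from the SAP 2.1 population, so that it matches the protocol estimand and the FAS.

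The cost is one further run of an existing program and a few sentences. The data should be to hand: protocol 6.7.2 collects dose, start and stop dates and the reason for stopping for UC therapies, and SAP 9.6.8 already plans to tabulate dose modifications of permitted therapy by arm.
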